Study Population:	We will recruit up to 72 males and non-pregnant females aged 18-65 with a diagnosis of lupus, free of benzodiazepines and anticonvulsant medications. We anticipate having evaluable data from at least 45 participants. Participants will be recruited in person from the UNC Rheumatology Specialty Clinic and through indirect recruitment from the surrounding Chapel Hill, Durham, and Raleigh areas.
Phase:	N/A
Description of Sites/Facilities Enrolling Participants:	University of North Carolina at Chapel Hill

[figure not shown]
Lupus Brain Protocol	Version 1.8 4 March 2022
-------------------------	-----------------------------

Description of Study Intervention:	Patients will be randomized with equal allocation into 3 study arms: an active sham, individualized alpha-tACS (usually 8-12 Hz), or individualized theta-tACS (individualized alpha frequency minus 4 Hz). Active sham treatment will include 20 seconds of ramp in to 40 seconds of 10Hz tACS with a ramp out of 20 seconds for a total of 80 seconds of stimulation. The choice of an active sham is motivated to enhance success of patient blinding by mimicking skin sensations associated with tACS. alpha-tACS and theta-tACS will also have a 20 second ramp in and ramp out with 40 minutes of stimulation for a total of 2440 seconds. Stimulation waveforms are sine-waves with an amplitude of 1mA zero-to-peak. Participants will stay in a relaxed yet experimentally controlled state by watching a nature movie such as “Reefscape” during stimulation.
Study Duration:	2 years

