3 OBJECTIVES AND OUTCOME MEASURES

OBJECTIVES	OUTCOME MEASURES	JUSTIFICATION
Primary		
To investigate the physiological changes in patients with systemic lupus erythematosus over the course of a 5-day, 40-minute stimulation protocol, specifically changes in alpha oscillation power from resting-state EEG recordings from baseline (Day 1) to Day 5 of stimulation.	Resting state EEG recordings taken on Day 1 and Day 5 of stimulation.	The protocol is for a 5-day intervention. The primary objective is focused on looking at the change in brain activity over the course of the intervention. Long-term effects (2-week follow-up and 4-week follow-up) will be assessed as exploratory outcomes.
Secondary		
To elucidate the relationship between changes in EEG and changes in pain and depression symptoms, by comparing the changes in symptoms and the change in alpha oscillation power over the course of the intervention (baseline to day 5 of stimulation). The SF-36 will be evaluated at screening and 4-week follow-up.	Correlations between clinical assessments and alpha oscillation power (as measured by resting state EEG recordings) from Day 1 and Day 5 of stimulation.	The objective is to target engagement (i.e., if the stimulation paradigm changes brain activity); the secondary objective is to determine if this engagement resulted in behavioral changes.
Exploratory		
To investigate the outlasting effects, if any, of tACS on brain activity and clinical assessments.	Resting state EEG recordings taken on 2-week and 4-week follow up visits.	The objective is to explore if any changes in brain activity persist as long-term effects. Long-term effects are detected at the 2-week and 4-week follow ups.
To investigate whether tACS increases cognitive control signals during cognitive tasks that probe sustained attention, selective attention, and working memory.	Correlations between frontal midline alpha and theta activity (as measured from EEG recordings on D1, D5, 2-week, and 4-week follow up visits) and accuracy at cognitive	We hypothesize that tACS will improve cognitive control. In particular, we hypothesize that alpha frequency tACS will improve performance the most for tasks that require attention (sustained attention and selective attention tasks),

Lupus Brain		Version 1.8
Protocol		4 March 2022

OBJECTIVES	OUTCOME MEASURES	JUSTIFICATION

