9.1.2 SECONDARY EFFICACY HYPOTHESIS

Null hypothesis: There is no relationship between the changes in alpha frequency power and the changes in depression (using the IDAS and HDRS), pain (using the comparative pain scale and pain catastrophizing scale), and cognition (using the sustained attention task, selective attention task, working memory task, and FSCMC).

Alternate hypothesis: There is a relationship between the changes in alpha frequency power and the changes in depression (using the IDAS and HDRS), pain (using the comparative pain scale and pain catastrophizing scale), or cognition (using the sustained attention task, selective attention task, and working memory task, and FSCMC).

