9.2 SAMPLE SIZE RATIONALE

At this point in time, no clinical trial has been completed using tACS to treat SLE. However, the Carolina Center for Neurostimulation has run several trials similar to this, including a clinical trial assessing the use of tACS to treat depression over the course of a 5-day, 40-minute stimulation paradigm (Alexander et al., 2019).

This study is a critically necessary preliminary step in this line of research. The most important aspects of the study are its exploratory analyses, its provision of point- and interval-estimates of parameters of interest, and the logistical feasibility and tolerability information it will provide. The levels of precision of the estimators of interest are important; e.g., based on a previous tACS intervention study (Alexander et al., 2019) with a mean alpha oscillatory difference of ~ 2 and $SD \approx 1.2$ and alpha set at .05, we anticipate $N=20$ per group will provide more than 80% power. The effect size was based off the difference between active tACS and sham stimulation. This study will also provide an initial indication of whether it is plausible that tACS may have beneficial effects for the target lupus population. Based on the anticipated

precision of estimators, power levels of test procedures, availability of research subjects, and stage of this line of research, we believe the study is likely to achieve its specific aims; i.e., there is low risk the study will be uninformative/inconclusive.

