9.4 STATISTICAL ANALYSES

9.4.1 GENERAL APPROACH

All testing described below assumes a significance threshold of $p = 0.05$. All hypothesis tests that are observed to not be statistically significant will be reported as being inconclusive. Continuous data will be described using means and standard deviations, while categorical data will be described using counts/percentages. All statistical estimates of population parameters will be tabulated along with their corresponding confidence intervals (CIs).

Sensitivity analyses will be used to evaluate the robustness of the main results to reasonable perturbations of the statistical models and assumptions used.

[name] will be responsible for statistical computations for data analyses. During the initial data analysis phase, [name] will be blinded to whether data and results are from sham vs active treatment in compliance with the UNC School of Medicine Conflict of Interest Committee proposed financial conflict of interest management plan.

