9.4.2 ANALYSIS OF THE PRIMARY EFFICACY OUTCOME MEASURE(S)

We will perform spectral analysis of resting state EEG from day 1 of stimulation (baseline) to day 5 of stimulation. We will use a general linear mixed-effects model (GLMM) to assess if there is statistically significant interaction between treatment (sham/placebo, theta-tACS and alpha-tACS) and session (baseline/Day 1 of stimulation, day 5 of stimulation, 2-week follow-up, 4-week follow-up). Spectral analysis will be performed with multitapered estimation of the frequency spectrum followed by integration over the classical alpha EEG band (usually 8-12 Hz). In a separate analysis, we will perform spectral analysis of resting state EEG before and after each separate stimulation session. These analyses will be completed on the per-protocol dataset.

In our previous study, which used a 5-day protocol in patients with depression (Alexander et al., 2019), we found that a correlation between the log-transformed baseline alpha power (dB) and the alpha power changes at the end of the intervention (Day 5) in all regions. We chose to use the log-transformed baseline alpha power as a covariate. We will use this same covariate in these analyses as well.

Results from this section will be described in mean decibel (dB) change and presented using spectral images for visualization.

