9.4.3 ANALYSIS OF THE SECONDARY OUTCOME MEASURE(S)

Using the EEG results described in 9.4.2, mean dB change from baseline will be correlated with normalized change in HDRS* as well as the other described measures. Correlations will be assessed using Pearson's r and data will be plotted against the best fit line to visualize the results.

*HDRS normalization:

$$\frac{[\text{HDRS score at Visit \#}] - [\text{HDRS score at baseline}]}{[\text{HDRS score at baseline}]}$$

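### The secondary alpha–symptom correlation has no arm term, so shifts in arm means alone can produce a correlation that does not show whether engagement led to symptom change

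*Combined protocol and SAP*

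**What the plan says.** Section 9.4.3 takes the alpha-power change from the EEG analysis and says "mean dB change from baseline will be correlated with normalized change in HDRS" and with the other measures. The method is one sentence: "Correlations will be assessed using Pearson's r and data will be plotted against the best fit line to visualize the results". Pearson's r takes two variables, and one line is to be drawn.

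The null hypothesis in Section 9.1.2 begins "There is no relationship between the changes in alpha frequency power and the changes in depression (using the IDAS and HDRS" and goes on to pain and cognition. It does not mention arm. Section 9.4.1 adds "All testing described below assumes a significance threshold of" p = 0.05, and a general promise of sensitivity analyses that names no arm adjustment.

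Treatment does enter the primary model in Section 9.4.2, which tests for a "statistically significant interaction between treatment (sham/placebo, theta-tACS and alpha-tACS) and session". It is not carried into Section 9.4.3. The synopsis says "Patients will be randomized with equal allocation into 3 study arms".

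The use of the correlation is stated in Section 3: "the secondary objective is to determine if this engagement resulted in behavioral changes".

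**The concern.** A correlation taken over three randomized arms mixes two things: whether participants with larger alpha change have larger symptom change within an arm, and whether the arm means of the two variables line up. The second can arise from two separate treatment effects. If stimulation moves alpha power, and symptoms also move in the same arms by another route (for example, a response that differs by arm because participants guess their allocation), r is non-zero even when no participant's alpha change predicts their own symptom change.

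The plan expects the ingredients. Section 9.2 assumes an EEG shift and says "The effect size was based off the difference between active tACS and sham stimulation", so it is a difference between arm means. Section 2.2 expects alpha-tACS to lower depression symptoms. What is at stake is a mechanistic conclusion, that engaging alpha oscillations changed symptoms, drawn from a statistic that cannot separate it from two parallel effects.

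**Working it through.** **Inputs.** From the plan: three arms, 1:1:1 (synopsis); at least 45 evaluable participants, so 15 per arm if balanced (Section 9.3); EEG difference about 2 with SD about 1.2 (Section 9.2); threshold 0.05 (Section 9.4.1), taken as two-sided. Assumed: a symptom shift of 0.2 to 1.0 SD, since the documents give none; normal changes with unit SD within arm; zero within-arm correlation unless stated.

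**The plan's own figure.** The standardized EEG shift is 2/1.2 = 1.67. With 20 per group the two-sample power is above 99.9%, so the plan's claim of more than 80% holds as an inequality. The plan gives no power, sample size or expected r for the correlations.

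**Population value of the unadjusted r.** With zero within-arm correlation,

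r = Cov(arm means of X, Y) / √[(1 + Var(arm means of X)) × (1 + Var(arm means of Y))].

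Example, one arm shifted by 1.67 SD (EEG) and 0.5 SD (symptoms):
- Covariance = (2/9) × 1.667 × 0.5 = 0.185
- Variances = (2/9) × 1.667² = 0.617 and (2/9) × 0.5² = 0.056
- r = 0.185 / √(1.617 × 1.056) = 0.14

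Shifting both active arms alike gives the same value. The sign is illustrative; r is negative if symptoms fall as alpha power rises.

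**Simulation, matched pattern** (20,000 trials per setting):

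| Symptom shift (SD) | Mean unadjusted r | Significant, 15 per arm | Significant, 20 per arm | Significant after arm adjustment |
|---|---|---|---|---|
| 0 | 0.00 | 5% | 5% | 5% |
| 0.3 | 0.09 | 9% | 10% | 5% |
| 0.5 | 0.14 | 16% | 19% | 5% |
| 0.8 | 0.22 | 31% | 40% | 5% |
| 1.0 | 0.27 | 43–44% | 54–55% | 5% |

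**Other patterns, 15 per arm** (shifts listed as sham, alpha, theta):
- EEG (0, 1.67, 1.67), symptoms (0, s, 0): the covariance halves to (1/9) × 1.667 × s. Significant in about 6%, 7%, 11% and 13–14% at s = 0.3, 0.5, 0.8 and 1.0.
- EEG (0, 1.67, 1.67), symptoms (0, s, −s), or EEG negative in both arms: the covariance is zero. Significant in about 4.2% at s = 0.5 and 3.5% at s = 1.0, so no inflation.
- EEG (0, 1.67, −1.67), symptoms (0, 0.5, −0.5): r = 0.556 / √(2.852 × 1.167) = 0.30; significant in about 56%.
- As the last, but with both variables shifted by only ±0.5 SD: r = 0.167 / 1.167 = 0.14; significant in about 15–16%.
- Smaller matched shifts: 0.5 SD in both variables gives r = 0.05 and 6.5%; 0.8 SD in both gives about 0.13 and 12.7%.

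**What adjustment costs if mediation is real.** Let symptom change depend on EEG change only, with within-arm r = 0.3 and the 1.67 SD EEG shift. At 45 participants the unadjusted r is significant in 73% of trials and the arm-adjusted one in 51%. At within-arm r = 0.4 the figures are 94% and 77%.

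**The case against.** Four points on the other side carry weight.

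First, a reader might infer that the test has an inflated Type I error. It does not, for the hypothesis as written. Section 9.1.2 states a marginal null, and in the inflated settings the marginal correlation is truly non-zero, so rejecting that null is correct. What fails is the step from that correlation to the claim in Section 3.

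Second, a reader might infer that any treatment effect on both variables creates the artefact. The shifts must also covary across arms, and the documents do not fix the pattern. Section 2.3.1 reports that alpha-tACS lowered alpha power over five days in the earlier depression trial, and proposes that theta-tACS would suppress alpha and might worsen depression; read that way, there is no inflation. Section 4.2 treats theta as the control frequency, which gives the mild pattern. Section 2.2 allows that theta might treat depression better than alpha, which is nearer the matched pattern. A placebo response common to all arms creates no artefact; only one that differs by arm does. The active sham is meant to prevent that, and Section 8.1.5 measures blinding.

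Third, if alpha change does mediate benefit, the between-arm part of r is signal. Adjustment discards the EEG variation that randomization created, so a reader should not conclude that the adjusted estimate ought simply to replace the unadjusted one. Within-arm EEG change is not randomized, so the adjusted r does not prove mediation either.

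Fourth, the plan never says that participants are pooled. That is inferred from the two-variable statistic, the single line and the arm-free hypothesis. The exact statement is that no arm term or within-arm analysis is specified.

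This is also a secondary analysis in a pilot that stresses estimation. That lowers the stakes, but an interval around the unadjusted r would still not estimate the within-arm association.

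**Conclusion.** The point stands as a gap between the analysis and its stated use. As specified, Section 9.4.3 can yield a significant correlation with no association within arms, and Section 3 would read it as engagement producing behavioral change. With 15 per arm and the plan's 1.67 SD EEG shift, this happens in about 9% to 43–44% of trials for matched symptom shifts of 0.3 to 1.0 SD, against 5% after adjustment. Across other patterns it runs from no excess to about 56%.

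The size rests on an assumed symptom shift, an assumed pattern across arms, and the plan's large EEG shift holding; with small shifts, or an EEG shift alone, it is minor or absent. The documents do not support the stronger readings that the stated null is tested at the wrong level or that the unadjusted r is worthless. It is a cheap improvement worth making before unblinding.

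**What to change.** Amend Section 9.4.3 to:
- state that the unadjusted r is computed over all per-protocol participants, if that is the intention;
- report beside it, for each measure, a partial correlation adjusted for arm (equivalently, a linear model of symptom change on dB change plus arm), with its CI;
- plot the data by arm;
- state that the unadjusted r alone will not be interpreted as evidence that engagement led to symptom change, and that neither estimate alone establishes mediation.

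Cost: SAP wording, no new data or visits, and two degrees of freedom (45 − 4 = 41 rather than 45 − 2 = 43). The further cost is lower power for the adjusted estimate if mediation is real, about 51% against 73% at within-arm r = 0.3. That is why the unadjusted r is kept.

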9.4.4 SAFETY ANALYSES

Safety will be assessed with a suicide questionnaire, the Columbia-Suicide Severity Rating Scale (C-SSRS), an adverse effects questionnaire, and the Young Mania Rating Scale (YMRS).

The suicide questionnaire is used as a screening to assess increase in suicidal ideation (SI) or suicidal behavior (SB). If a participant's responses indicate SI or SB, the participant will be contacted and an acute assessment will be completed if necessary by [name]. Any verified increases in suicidal ideation will be described in counts/percentages and compared between groups using chi-square tests.

The adverse effects questionnaire will be administered following every stimulation session, for a total of 5 administrations per participant. The adverse effects questionnaire inquires about 14 possible adverse effects associated with electrical stimulation, rated on a scale of 1 (absent) to 4 (severe). Paired t-tests

with random effect "participant" will be calculated per adverse effect to determine if there are any differences in adverse effect severity between groups (sham/placebo, alpha-tACS, theta-tACS). Severity per adverse effect will be described with mean and standard deviation.

The Young Mania Rating Scale (YMRS) will be used to assess any development of mania over the course of treatment. A YMRS score of greater than 12 indicates the possible development of a manic episode. Any participant who scores greater than 12 on the YMRS will be assessed by [name]. Any verified manic episode will be described in counts/percentages and compared between groups using a chi-square test.

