1.2.1 ARM ALLOCATION

Up to 72 participants will be equally randomized in to one of three arms (1:1:1):

**Randomization is double-blind

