Risk of Injury and Discomfort: The side effects of tACS are mild and transient; in fact, low intensity transcranial current stimulation, such as tACS, has been used for several years without any report of serious side effects ([name] & McCormick, 2010). Furthermore, this stimulation mode has nothing to do with electroconvulsive therapy that applies many orders of magnitude higher stimulation current. Rather, transcranial current stimulation is so weak that it does not cause super-threshold activation of neurons (Khan, Khan, Shankles, & Polissar, 2002). However, tACS does have some mild side effects, such as transient mild tingling, burning, or itching under the electrode sites. In the first part of this study, participants from all three groups reported either absent or mild side effects and there was no difference between the groups with the exception of "flickering lights" (or phosphene, $p = 0.014$) (Alexander et al., 2019). In order to monitor these, we will be administering an adverse effects stimulation questionnaire after each stimulation session to determine whether these effects were experienced and at what intensity. Research personnel present during these sessions will also check in with the participant periodically during the stimulation to see whether they are comfortable. If participant is experiencing severe discomfort (as determined by the adverse effects questionnaire or by self-report), the stimulation will be immediately stopped.

Risks associated with emotional distress in case of incidental findings on structural MRI or a false positive pregnancy test.

Risks associated with venous blood draw include minimal discomfort and/or bruising. Infection, excess bleeding, clotting, and fainting are also possible, although unlikely.

Patients experiencing depression have a higher risk of suicide. We have no evidence that our treatment paradigms will in any way increase this likelihood. In a similar study in patients with major depressive disorder (MDD), 4 participants in the sham/placebo stimulation group experienced an increase in suicidal thoughts and only one of those 4 participants reported suicidal intent. No participants who

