4 STUDY DESIGN

4.1 OVERALL DESIGN

The design for this study is a pilot, randomized, double-blind, sham-controlled clinical trial which will be used to investigate the effects of alpha-tACS on patients with systemic lupus erythematosus (SLE), as well as determine the relationship between physiological changes and clinical changes. We are recruiting from a clinical population. For this trial, we are seeking up to 72 males and non-pregnant females, ages 18-65, with a diagnosis of SLE, free of benzodiazepines and anticonvulsant medication, and at a low risk for suicide according to the Hamilton Depression Rating Scale (HDRS17). We anticipate having evaluable data from at least 45 participants. All women of child-bearing potential will be asked to take a pregnancy test during the initial session in order to determine eligibility for the study; nursing or pregnant participants will be excluded from participation and all women of child-bearing potential will be required to use an appropriate form of birth control throughout their participation. These individuals will be outpatients and may seek mental health care from a family practitioner, therapist or psychiatrist.

This is a single-site, pilot clinical trial with 3 arms of equal allocation (1:1:1). We estimate 2 years to complete study enrollment. Participants will be randomly assigned to one of three arms; active sham stimulation, individualized alpha-tACS (usually 8-12Hz), or individualized theta-tACS (alpha frequency minus 4 Hz). Active sham stimulation will include 20 seconds of ramp-in to 40 seconds of 10 Hz tACS with a ramp out of 20 seconds for a total of 80 seconds of stimulation. The choice of an active sham is motivated to enhance success of patient blinding by mimicking skin sensations associated with tACS. Alpha- tACS and theta-tACS will have a 20 second ramp-in and ramp-out with 40 minutes of stimulation for a total of 2440 seconds of stimulation. Stimulation waveform is a sine-wave with an amplitude of 1 mA. In each arm, participants will stay in a relaxed and yet controlled state by watching a nature movie such as “Reefscape” during stimulation.

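### Section 9.4.4 relies on chi-square tests alone for suicidal ideation and mania; if events are few, the p-value for the observed table can be about half the exact one

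*Combined protocol and SAP*

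**What the plan says.** Section 9.4.4 (Safety Analyses) handles two rare binary safety outcomes in the same way. For suicidal ideation: "Any verified increases in suicidal ideation will be described in counts/percentages and compared between groups using chi-square tests". For mania: "Any verified manic episode will be described in counts/percentages and compared between groups using a chi-square test". Section 9.4.1 sets the significance threshold at 0.05 for all tests.

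No exact test, small-count rule or descriptive fallback is named for these outcomes. Section 9.4.1 promises confidence intervals for all estimates and sensitivity analyses of the model assumptions, but names no method for either. It also says that non-significant tests will be reported as inconclusive.

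On arm size, section 1.2.1 randomizes up to 72 participants 1:1:1, section 9.2 works with 20 per group, and section 4.1 says: "We anticipate having evaluable data from at least 45 participants".

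On event frequency, section 2.3.1 reports that in a similar study in major depression "4 participants in the sham/placebo stimulation group experienced an increase in suicidal thoughts" and that no tACS participant did. It gives no denominator. Section 2.2 cites suicidal ideation in up to 25% of SLE patients, which is a background prevalence. Entry is limited to low suicide risk (5.1), bipolar or manic history is excluded (5.2), and section 8.2.1 does not expect mania to occur.

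**The concern.** The chi-square p-value is a large-sample approximation, usually trusted when expected cell counts are about 5 or more. With three arms of 15 to 24 and an uncommon event, expected counts may fall far below that, and the printed p-value then differs from the exact probability of the table.

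Two or three events clustered in one arm is a pattern these comparisons may well have to judge. A p-value on the wrong side of 0.05 could create or overstate a between-arm suicidality signal, for or against an active arm. Section 9.2 lists tolerability among the study's most important products, and section 2.3.1 raises the possibility that theta-tACS could worsen depression, so readers will look at these results.

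**Working it through.** **The plan's own figure.** The documents give no calculation for the safety tests. The only computed claim is for the EEG outcome: "we anticipate $N=20$ per group will provide more than 80% power", with a difference of about 2 and an SD of about 1.2. A two-sided two-sample calculation at 0.05 gives power 0.9995, so the claim holds as a lower bound. It does not bear on this point.

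**Inputs.** Three equal arms of n = 15 (45/3), 20 (section 9.2) or 24 (72/3). The total number of events, T, is not given, so it is varied.

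**Expected events per arm, T/3.**
- T = 3 gives 1.0, and T = 4 gives 1.33.
- One or two manic episodes give 0.33 or 0.67.
- All three expected event counts reach 5 only when T is 15 or more.
- If the 25% background prevalence were the on-study rate: 15 × 0.25 = 3.75, 20 × 0.25 = 5.0, 24 × 0.25 = 6.0.

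**Chi-square p-value.** With e = T/3, X² = Σ(xᵢ − e)²/e + Σ(xᵢ − e)²/(n − e). With 2 df, p = exp(−X²/2). At n = 15:
- 3-0-0: 6/1 + 6/14 = 6.43, p = 0.040.
- 4-0-0: 10.667/1.333 + 10.667/13.667 = 8.78, p = 0.012.
- 5-2-0: 12.667/2.333 + 12.667/12.667 = 6.43, p = 0.040.

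**Exact p-value (Fisher-Freeman-Halton).** Sum the probabilities of all tables with the same T that are no more probable than the observed one. At n = 15:
- 3-0-0: 3·C(15,3)/C(45,3) = 1365/14190 = 0.096.
- 4-0-0: 3·C(15,4)/C(45,4) = 4095/148995 = 0.028 (0.0275).
- 5-2-0: the patterns 7-0-0, 6-1-0 and 5-2-0 in every arm order give (19305 + 450450 + 1891890)/45379620 = 0.052.

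**Chi-square against exact p at each arm size**

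| Split | n = 15 | n = 20 | n = 24 |
|---|---|---|---|
| 2-0-0 | 0.123 / 0.318 | 0.126 / 0.322 | 0.128 / 0.324 |
| 3-0-0 | 0.040 / 0.096 | 0.043 / 0.100 | 0.044 / 0.102 |
| 4-0-0 | 0.012 / 0.028 | 0.014 / 0.030 | 0.015 / 0.031 |
| 5-2-0 | 0.040 / 0.052 | 0.046 / 0.058 | 0.0495 / 0.062 |

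The 3-0-0 and 5-2-0 splits change sides of 0.05 at every arm size; 2-0-0 and 4-0-0 do not.

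**Rejection rate given T (n = 15, no true difference).**
- T = 3: chi-square rejects 9.6% of the time, the exact test never.
- T = 1 or 2: neither test can reject.
- T = 4, 5, 6, 8, 9 or 10: the two tests have identical rates.
- T = 7, 11 and 12: chi-square rejects 5.2%, 6.9% and 5.5%.

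**Long-run type I error (averaging over T ~ Binomial(45, p), n = 15).** Chi-square size is 0.5% at a 2% event rate, 2.4% at 5%, 3.1% at 6.67% (one expected event per arm; exact test 0.8%) and 5.0% at 25%. The maximum over common rates from 0.5% to 50% is 5.2%.

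**Power cost of the exact test.** Assume true rates of 0%, 0% and 20% with n = 15, so that all events fall in one arm. Chi-square rejects from 3 events upward: P(Bin(15, 0.2) ≥ 3) = 60%. The exact test needs 4: P(Bin(15, 0.2) ≥ 4) = 35%. At 20 per arm the figures are 79% and 59%; at 24 per arm, 89% and 74%.

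**The case against.** The best defence of the plan is that chi-square does no general harm here. Averaged over event totals, its false-positive rate is near or below the nominal 5%, and it has more power than the exact test. For a suicidality signal, missing a real difference may be the costlier error. Conditional against unconditional testing is a recognised choice. All of this stands, and it means the change has a price.

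Other parts also stand. The study is a pilot. No stated decision depends on these p-values: interim DSMB reports are descriptive (9.4.6), and suspension follows event-count rules (7.4). Section 9.4.1 already promises confidence intervals and treats non-significance as inconclusive. With no events the chi-square statistic is 0/0, but the exact test is equally uninformative (p = 1).

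A reader might infer three stronger things that the documents do not support:
- **That the planned tests inflate the trial's false-positive rate.** They do not; the 9.6% applies only when exactly 3 events occur.
- **That the earlier study's pattern would be misjudged.** A 4-0-0 split is below 0.05 under both tests.
- **That expected counts of about 1 are a fact of the plan.** They follow from an assumed 3 to 4 events; at the 25% prevalence with 20 or 24 per arm they reach 5 or 6.

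The defence does not answer the narrower point. The report will print one p-value for one observed table, and in a sparse table that value can be about half the exact one. A general promise of intervals and sensitivity analyses does not say how this will be handled.

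**Conclusion.** The point holds as a cheap improvement. If events number about 3 to 7 in total, the chi-square p-value in 9.4.4 may be too small for the table observed, and some splits (3-0-0, 5-2-0) switch from significant to non-significant under the exact test at every arm size in the documents. The size is 0.040 against 0.096 in the clearest case and 0.040 against 0.052 in a marginal one; many other tables give the same decision either way. Long-run type I error is not materially affected.

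This rests on equal arms of 15 to 24, an event total that the documents do not state, and a two-way comparison of arm by event with 2 df. Mania is likely to be sparser than ideation, given the exclusions and the protocol's own expectation.

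**What to change.** In section 9.4.4:

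1. Replace both chi-square tests with the Fisher-Freeman-Halton exact test.
2. When an outcome has no events, report counts only, without a test.
3. Make the main presentation each arm's proportion with a Clopper-Pearson 95% CI, plus the alpha-sham and theta-sham risk differences with exact CIs. The method should be named because a normal-approximation interval has zero width at 0 events, whereas the Clopper-Pearson upper limit for 0 of 15 is 1 − 0.025^(1/15) = 21.8%.
4. State that a non-significant exact test is not evidence of safety and that the intervals carry the interpretation.

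The cost is a few sentences, with no change to data collection or conduct. The statistical price is a conservative test: size 0.8% at one expected event per arm, and power of 35% instead of 60% in the scenario above. That loss is why items 3 and 4 belong with the change of test.
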